## **STUDY PROTOCOL**

### **1. BACKGROUND AND RATIONALE**

#### **1.1. General Introduction**

It is common practice in the United States and other countries worldwide to perform a detailed ultrasound to assess fetal anatomy, usually in the second trimester (18 weeks to 22 weeks gestational age). This time period makes ultrasound scans feasible to perform and interpret, because the fetus is large enough, and organ systems are well developed. Increasingly sophisticated ultrasound technology has prompted earlier scans, and first trimester anatomy ultrasound has become more feasible, even for complex organs such as the fetal heart. In some prospective cohort studies, first trimester ultrasound offers equivalent imaging to second trimester ultrasound in obese patients, who are difficult to scan abdominally in the second trimester due to the layer of adipose tissue between the ultrasound transducer and the fetus.

Obese women have lower rates of successful second trimester anatomy ultrasounds than do lean women. Difficult second trimester anatomy scans lead to suboptimal views and repeated scans, which has financial, emotional, and logistical costs. Fetal anatomy in these patients can be evaluated in the first trimester of pregnancy by ultrasound either transabdominally through the smaller layer of adipose at the pubic symphysis, or transvaginally. First trimester ultrasound has been studied in prospective cohort trials, it is safe and provides clear anatomic views, but randomized studies are necessary to determine whether this technique can decrease the number of scans required to completely evaluate the fetal anatomy in obese patients, without missing major anomalies.

This study aims to fill that gap by studying if first trimester anatomy ultrasound can significantly contribute in the fetal anatomic evaluation in obese patients, and to establish whether it is a complementary or an alternative technique to second trimester anatomy ultrasound for this population.

**b. Rationale for Study Population**

A BMI(Kg/M) of  $\geq 35$  was chosen as the primary inclusion criteria given that the rate of completion of second trimester anatomy ultrasound does not significantly differ between women of BMI  $< 35$ , whether lean, overweight, or obese (7). The study population include women of child-bearing age and fetuses, even though these populations have some vulnerabilities, because it is designed to study an aspect of pregnancy.

**c. Rationale for Study Design**

Several cohort studies of first trimester ultrasound already exist (16, 17), but no randomized data is available. For these techniques (first and second trimester ultrasound) to be adequately compared, a randomized design is necessary. Other designs, such as before-and-after and prospective cohorts were considered, but given that this is a relatively simple intervention to directly compare, and randomization offers significant objectivity, a randomized controlled trial is proposed.

**d. Rationale for Dating Ranges and Images Required**

Required images in the first trimester anatomy ultrasound (the intervention) were selected based on peer-reviewed literature on the subject of early fetal anatomy assessment. A detailed list of images required in the intervention is appended. The following is a list of required planes and peer-reviewed literature to support their use as key in the evaluation of major and minor fetal anomalies. This list of planes is deemed sufficient by multiple experts in the field and the International Society for Ultrasound in Obstetrics and Gynecology, or ISUOG (14, 19).

1. Midsagittal fetus
2. Placental cord insertion
3. Profile
4. Lateral ventricles
5. BPD (transthalamic view)
6. Head circumference
7. Posterior fossa (cerebellum)
8. Orbita
9. Face (including retronasal triangle)
10. Heart rate
11. Situs
12. Four chamber heart
13. 3 vessel view
14. Bladder
15. Kidneys
16. Abdominal circumference
17. Fetal cord insertion
18. 3 vessel cord
19. Extremities
20. Spine

The first trimester required images largely correspond with second trimester required images, with very few differences which reflect that some structures (e.g. the lip) are hard to see in the first trimester, and are replaced by a feasible alternative (e.g. the retronasal triangle) based on peer-reviewed literature.

IRB NUMBER: HSC-MS-20-0895  
IRB APPROVAL DATE: 08/12/2021

All ultrasounds performed in the second trimester, both the GSS for the intervention arm and the anatomy evaluation in the comparison arm, will be evaluated for completion based on UT's proprietary second trimester protocol, which abides by standards set out by the International Society of Ultrasound in Obstetrics & Gynecology (ISUOG) and the American Institute of Ultrasound in Medicine (AIUM) (20, 22-23). A list of images required for the comparison is given here in brief.

1. Fetal position
2. Placental cord insertion
3. Profile
4. Lateral ventricles
5. BPD (transthalamic view)
6. Head circumference
7. Posterior fossa (cerebellum)
8. Choroid plexus
9. Orbita
10. Face
11. Nose-lips
12. Heart rate
13. Heart rate
14. Situs
15. Four chamber heart
16. 3 vessel view
17. Interventricular septum
18. Bladder
19. Kidneys
20. Abdominal circumference
21. Fetal cord insertion
22. 3 vessel cord
23. Diaphragm

24. Extremities (including femur length, humerus length, hands, feet)

## **2. HYPOTHESIS AND OBJECTIVES**

### **2.1. Hypothesis**

1. An ultrasound evaluation in the late first trimester (12w0d to 13w6d) is more likely to provide a complete fetal anatomical evaluation than an ultrasound evaluation done in the second trimester (18w0d to 22w6d) of pregnancy in obese women.
2. Ultrasound evaluation of fetal anatomy in the first trimester (12w0d to 13w6d) *combined with* conventional ultrasound evaluation of fetal anatomy in the second trimester (18w0d to 22w6d) will provide with more information than either in isolation.

### **2.2. Primary Objectives**

Assess the feasibility of ultrasound in the first trimester at our Center with our equipment and personnel. Assess the completion rate of ultrasounds for fetal anatomy in the first trimester (12w0d to 13w6d) compared to completion rates of ultrasounds for fetal anatomy in the second trimester (18w0d to 22w6d) in obese women.

### **2.3. Secondary Objectives**

Assess the completion rate of the *combination* of one ultrasound in the first trimester and one in the second trimesters (12w0d to 13w6d *and* 18w0d to 22w6d), compared to the individual completion rates of both evaluations in obese women.

### **2.4. Primary Outcome**

The primary outcome is the completion rate (number of scans that see all the views listed on pages 7 or 8 divided by total number of scans in that group) for first trimester ultrasounds, compared to the same metrics obtained in second trimester ultrasounds.

### **2.5. Secondary Outcome**

Secondary outcomes include:

1. Completion rate of both first and second trimester scans (when considered as a single instrument to visualize the fetal anatomy, what is the rate of complete visualization divided by all women?)
2. Total length of scanning time in the first trimester ultrasound group
3. Number of anomalies identified (and missed) in each group
4. Neonatal outcomes (survival, gestational age at delivery, NICU admission, hospital LOS, neonatal morbidities including respiratory distress syndrome, transient tachypnea of the newborn, intraventricular haemorrhage, necrotizing enterocolitis)
5. Patient feedback to standardized surveys (see attached)

6. Cost of intervention compared to usual care (cost benefit analysis based on whether more ultrasounds were done in cases of early discovery of anomalies)

**a. End Points - Efficacy**

Anticipated benefits of first trimester detailed anatomy scan include a higher completion rate the initial ultrasound performed for anatomy. We anticipate that this will decrease the number of times future obstetric patients will have to return for additional ultrasounds. There will be no direct benefits to the participants in the prior trial apart from the intervention arm gaining an additional look at their baby, which may have potential social or psychological benefits.

**b. End Points – Safety**

Anticipated risks of ultrasound are low. While there is theoretical risk of the effects of high-output ultrasound techniques, such as color Doppler, causing increased core body temperature and possible teratogenic effects in the first trimester, there is not a well-accepted incidence of ultrasound-related fetal adverse outcomes, and ultrasound is generally deemed of low or no risk by professional organizations (21). Available guidelines suggest that judicious clinical use of ultrasound as appropriate to the patient risk profile should be employed (19-23).

Of note, expert opinion on this matter deems all patients included in this study as high risk for anatomic abnormalities (14), which justifies detailed investigation, including Doppler ultrasound.

**3. STUDY POPULATION**

Broadly speaking, the population is obese pregnant women with  $BMI \geq 35$  ( $Kg/M^2$ ).

**3.1. List the number of subjects to be enrolled.**

A sample size of 118 women was calculated based on the primary outcome of initial scans which completely clear the fetal anatomy (see below for details of sample size calculation). It is necessary to include women in this study as this proposes a technique only possible in pregnancy. Minorities will be included to strengthen external validity of the study. Children will not be recruited.

**3.2. Criteria for Recruitment**

Once a potential subject expresses interest in participation, she will be asked to undergo a brief ultrasound to verify her gestational age. This ultrasound will be free of charge, will take approximately 5 minutes, and will not be entered in her medical record or saved as study images. This is to confirm viability gestational age, and number of fetuses.)

**3.3. Inclusion Criteria**

The subject must meet all of the following inclusion criteria to participate in this study:

- $BMI \geq 35$
- Age 18-50 years

- Presented for ultrasound before 14 weeks at UT Professional Building, Memorial City, Bellaire, or Lyndon-Baines Johnson clinics
- Primary language is English or Spanish
- Consent to an extra transvaginal ultrasound if needed
- Singleton gestation
- No previous anomalies known before consent
- Missed abortion (nonviable pregnancy)

Missed abortion will be defined by ultrasound findings during recruitment according to Doubilet et al 2013 (18), which is the widely-accepted standard in the United States.

### **3.4. Exclusion Criteria**

All subjects meeting any of the following criteria at baseline will be excluded from analysis, although will be reported as part of study flow:

- Elective abortion after recruitment
- Missed abortion after first trimester ultrasound
- Did not receive second trimester ultrasound

Missed abortion will be defined by ultrasound findings during recruitment according to Doubilet et al 2013 (18), which is the widely-accepted standard in the United States.

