#### **4.2. Study Flow Diagram**

#### **4.3. Study Visits and Procedures**

##### *a. Screening Visits and Procedures*

Research staff will screen the schedules of the ultrasound clinics at Memorial City, Bellaire, UT Professional Building, LBJ, and Harris Health Aldine ultrasound clinics for patients undergoing clinically indicated ultrasounds before 14 weeks gestational age. (These existing clinic visits are usually for dating ultrasound or nuchal translucency, an early assessment of a marker of aneuploidy.) Research staff will approach patients at these visits and describe the study. If the patient is interested in participation, the sequence of events that should occur include confirmation of eligibility with a 5-minute ultrasound to determine a single viable fetus before 14 weeks. This is the only procedure necessary before recruitment. If the patient is eligible according to this screening ultrasound, she can be randomized at that time.

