trimester ultrasound by the clinical team as part of standard obstetrical care and completes a survey regarding her satisfaction with this technique via email. Research staff will ensure patients have this scan scheduled and completed, as it is part of study procedure. Data about this scan will be recorded in the patient's research record. This scan can be repeated as indicated according to UT's protocol for assessing anatomy.

*c. Final Study Visit:*

The final study visit is denoted by completion of the second trimester gold standard scan (GSS) for patients randomized to the intervention arm, and at the completion of the second trimester anatomy ultrasound for patients randomized to the comparison arm. Participants will continue to be followed through their pregnancy to document the number of ultrasounds required to complete the fetal anatomy evaluation.

*d. Post Study Follow up and Procedures*

Medical records will be reviewed after each study participant's due date to assess whether delivery has occurred and to record delivery outcomes from the medical records, when available. This is chiefly so that a post-natal evaluation can be recorded to confirm or exclude anatomical anomalies. Delivery outcomes are not a primary outcome and request of outside delivery records will not be required for a subject's record to be marked as completely collected.

Adverse outcomes, including discomfort during ultrasound as well as neonatal outcomes, will be recorded in the subject's research record.

*e. Discontinuation Visit and Procedures*

Subjects may withdraw voluntarily from participation in the study at any time. Subjects may also withdraw voluntarily from receiving the study intervention for any reason.

If a patient in the intervention arm withdraws from the study during to her first trimester anatomy ultrasound, she will be asked to complete the survey regarding her experience regardless of the duration of the first trimester ultrasound. She will then undergo her clinically indicated ultrasound (which are not transvaginal).

If a subject in the intervention arm withdraws from the study prior to her second trimester GSS ultrasound (done as "back up" for the intervention), a standard email will be sent to her confirming her withdrawal and encouraging her to seek a second trimester (standard of care) anatomy ultrasound as the anatomy evaluation she had in the first trimester is considered experimental.

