## **9.2. Statistical and Analytical Plans**

Analysis will be carried out according to the intention-to-treat principle. All randomized subjects will be included in analyses for which they have data. Frequentist statistics will be reported, including mean number of scans in each group (compared with t tests, with ANOVA between classes of obesity), the proportion of complete scans in each group (compared with chi square test), and the mean total scan time (t tests). Secondary outcomes will also be analysed with a frequentist approach. Descriptive statistics will also be provided about anomalies found and missed (anticipated to be low, so likely few significant findings to report). In addition, patient perspectives will be described.

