**Withdrawal Email 1 (for intervention arm, withdrawing during her detailed first trimester ultrasound)**

Dear [Name],

We are sorry to see you go! Thank you for considering EASE-O, a randomized clinical trial to find out when is the best time for a detailed anatomy ultrasound in women with a BMI of 35 or greater. This email confirms that you have withdrawn from the study. Your data will not be analyzed and no further data will be collected.

You do not have to do anything further, but we ask that you tell us about your experience during your ultrasound, at [this link](#). Filling out this survey helps us understand what women like you prefer regarding their ultrasounds. We want to hear from you!

Sincerely,

[name]  
Principle Investigator, EASE-O

**Withdrawal Email 2 (for intervention arm, withdrawing after her detailed first trimester ultrasound, before her safety second trimester ultrasound)**

Dear [Name],

We are sorry to see you go! Thank you for participating in EASE-O, a randomized clinical trial to find out when is the best time for a detailed anatomy ultrasound in women

with a BMI of 35 or greater. This email confirms that you have withdrawn from the study. Your data will not be analyzed and no further data will be collected.

You do not have to do anything further, but we encourage you to seek out an ultrasound between 18 and 22 weeks gestational age, if you haven't already gotten one. You did have an ultrasound in the first trimester looking at all the baby's parts, but these ultrasounds are still considered experimental (that's why we are researching them)! You deserve a later ultrasound, it is still recommended and will be covered by your insurance as part of your routine prenatal care.

Sincerely,

[name]  
Principle Investigator, EASE-O

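### Section 3.4 excludes women from analysis for events after randomisation, while 2.4 and 9.2 keep them, so the primary analysis set is not fixed; the direction and size of any bias are unknown

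*Combined protocol and SAP*

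**What the plan says.** Section 3.4 opens: "All subjects meeting any of the following criteria at baseline will be excluded from analysis, although will be reported as part of study flow". Three criteria follow: elective abortion after recruitment, missed abortion after the first-trimester scan, and "Did not receive second trimester ultrasound".

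On timing, section 4.3 a says of a woman seen before 14 weeks: "If the patient is eligible according to this screening ultrasound, she can be randomized at that time".

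On analysis, section 9.2 adopts intention-to-treat and adds: "All randomized subjects will be included in analyses for which they have data". Section 2.4 defines the primary outcome as the number of complete scans "divided by total number of scans in that group". The intervention arm contributes its scan at 12w0d to 13w6d and the comparison arm its scan at 18w0d to 22w6d. Section 1.2 a describes the intervention arm's second-trimester scan as a backup against missed anomalies.

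On withdrawal, all three standard withdrawal emails tell the woman: "Your data will not be analyzed and no further data will be collected". Email 1, for withdrawal during the first-trimester scan, then continues: "we ask that you tell us about your experience during your ultrasound". Section 4.3 e treats leaving the study and leaving the intervention as separate acts: "Subjects may also withdraw voluntarily from receiving the study intervention for any reason". Section 7.2 scores an exam stopped at the patient's wish on the images already obtained. Section 3.6 replaces women who withdraw and is silent on women excluded under 3.4.

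**The concern.** The 3.4 criteria are labelled as baseline criteria, but each is worded as something that happens later. A second-trimester scan cannot be known to be missing until weeks after randomisation. Excluding randomised women for such events is what an intention-to-treat analysis is meant to prevent, and no text reconciles 3.4 with 9.2.

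The no-second-scan rule also works differently in the two arms. An intervention-arm woman who misses that scan normally has her primary outcome on record already, and 3.4 erases it. A comparison-arm woman who misses it never had one.

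Two things are at stake. First, two incompatible rules define who is in the primary analysis, so the choice could be made after the results are seen. Second, if missing the second scan is related to whether the first was complete, the intervention-arm completion rate could shift.

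The emails raise a related problem: a woman may have a scored scan that 9.2 would analyse and that the email says will not be analysed.

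**Working it through.** **Which rule keeps whom**

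| Randomised woman | 2.4 and 9.2 | 3.4 |
|---|---|---|
| Intervention, first-trimester scan scored, no second-trimester scan | counted | dropped |
| Comparison, no second-trimester scan | no primary outcome | dropped |
| Either arm, elective abortion after her primary-outcome scan | counted | dropped |

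The sections agree in effect only on the second row. The one-arm loss of observed outcomes belongs to the no-second-scan rule. An elective abortion after the second-trimester scan would discard an observed outcome in the comparison arm too.

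**Time between the two primary-outcome scans.** Shortest: 18w0d − 13w6d = 4w1d. Longest: 22w6d − 12w0d = 10w6d. An excluding event in that interval removes an observed primary outcome only in the intervention arm.

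**Inputs from the plan.** There are 19 + 20 + 20 = 59 women per arm (4.1), a 70% usual completion rate and alpha 0.05 (9.1), and a chi-square test (9.2). The recruitment arithmetic in 9.1 is 236 × 50% = 118, which leaves no allowance for loss.

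**One woman.** 41/59 = 69.5%. Dropping one incomplete scan gives 41/58 = 70.7%; dropping one complete scan gives 40/58 = 69.0%.

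**Type I error under assumed loss.** The method is exact binomial enumeration with an uncorrected chi-square test, two-sided 0.05, and true completion 70% in both arms. With no loss the result is 5.2%. Let g be the share of incomplete (or complete) scans whose women are lost; women lost are assumed not to be replaced. The number analysed is averaged over its binomial distribution. The observed completion rate in an arm with loss is

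- incomplete scans lost: 0.70 / (0.70 + 0.30(1 − g))
- complete scans lost: 0.70(1 − g) / (0.70(1 − g) + 0.30)

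| Assumed loss g | Observed rate in an arm with loss | 3.4, loss in intervention arm only | 3.4, same loss in both arms | 2.4/9.2 rule, same loss in both arms |
|---|---|---|---|---|
| 5% of incomplete | 71.1% | 5.3% | 5.1% | 5.3% |
| 10% of incomplete | 72.2% | 5.9% | 5.1% | 5.9% |
| 20% of incomplete | 74.5% | 8.4% | 5.1% | 8.4% |
| 5% of complete | 68.9% | 5.3% | 5.1% | 5.3% |
| 10% of complete | 67.7% | 5.9% | 5.1% | 5.9% |
| 20% of complete | 65.1% | 8.8% | 5.1% | 8.8% |

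In the last column the intervention arm keeps all 59 women because their scans were observed, while the comparison arm loses those never scanned. The imbalance is that of the third column with the arms exchanged, so the figures match. If only the intervention arm misses second scans, the 2.4/9.2 rule loses nobody and stays at 5.2%.

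**Loss unrelated to completeness.** Both rules stay near 5.1%. The cost of 3.4 is then only women: 59 × 0.95 = 56.1 or 59 × 0.90 = 53.1 analysed in the intervention arm, against 59 under 9.2.

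**Counting unscanned women as not complete.** With loss in the comparison arm only, unrelated to completeness, that arm's rate becomes 70% × (1 − loss): 66.5%, 63.0% or 56.0% at 5%, 10% or 20% loss. Type I error becomes 7.1%, 12.7% or 34.8%, nearly all of it favouring first trimester. That rule suits a sensitivity analysis and not the primary one.

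**The case against.** The strongest reply is that 3.4 applies to both arms. If missing the second scan does not depend on assignment, requiring that scan everywhere compares like with like, and the type I error stays at about 5.1%. The documents lean somewhat that way: first-trimester results are disclosed only for an anomaly (4.3 b and section 6), and staff ensure that the second scan takes place in both arms (4.3 b). This stands, and it means that the available-case rule of 2.4 and 9.2 has an asymmetry of its own.

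Other replies stand in part.

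- A note under 3.4 ties missed abortion to ultrasound findings at recruitment, and viability is checked before randomisation. It is therefore unclear which women that criterion covers.
- Combined completion (2.3 and 2.5) needs both scans, so a second-scan requirement may be legitimate there, although 2.5 divides by all women.
- What may be kept after withdrawal depends on the consent form, which was not available for review. Section 7.2 does not expressly cover a woman who leaves the study during the scan. The survey request in email 1 has no bearing on the primary analysis.
- Replacement under 3.6 is not in itself a breach of intention-to-treat.

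None of this answers the central point: for the intervention-arm woman without a second scan, the plan gives two answers.

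**Conclusion.** The contradiction between 3.4 and the pair 2.4 and 9.2 is certain from the text. It leaves the primary analysis set open and should be fixed before analysis. The email conflict is related but less firm, because it turns on the consent terms.

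A reader might infer that 3.4 biases the trial towards first-trimester scanning, or that replacing it would lower the type I error. The documents support neither. No loss rate is given, nothing states how attendance at the second scan relates to completeness of the first, and the shift could go either way. In the illustration, which rule looks worse depends on whether informative loss falls in one arm or in both. At 5% or 10% of incomplete scans lost, the excess is under one percentage point in either case.

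The case for change therefore rests on three things: it keeps outcomes already observed, it follows the intention-to-treat rule that the plan states, and it fixes one analysis set in advance. All error rates above rest on assumed losses.

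**What to change.** Make 9.2 govern the primary analysis. Analyse by assigned arm every randomised woman whose primary-outcome scan was performed, and remove the 3.4 post-randomisation exclusions from that analysis. Report women without a primary-outcome scan by arm, with reasons. Clarify which women the missed-abortion criterion covers.

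Prespecify two sensitivity analyses:

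- (a) the 3.4 set, requiring the second-trimester scan in both arms, which guards against informative loss common to both arms;
- (b) women without a primary-outcome scan counted as not complete.

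Limit any second-scan requirement to these and to the combined-completion secondary outcome, and reconcile it with that outcome's denominator in 2.5.

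For future withdrawals, reword the emails so that data collected beforehand are kept where consent allows. Score a stopped scan on the images obtained, as in 7.2. Reconcile email 1 with its survey request. Report withdrawals and replacements by arm.

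The cost is wording changes, an IRB amendment and some extra analysis; no new data collection is needed. Data of women already told that they would not be analysed stay out. The available-case primary rule can itself be biased if loss in the comparison arm is informative, which is why analysis (a) is needed beside it.
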